## **6. SELECTION OF STUDY POPULATION**

A total of 36 subjects will be required to complete the study. Of the 36 subjects, 24 are to be 18-65 years and 12 are to be >65 years of age. An attempt will be made for 50% male and 50% female enrollment.

The study is to be conducted in adult smokers and therefore participants may receive therapeutic benefit from taking part. Outside of being active smokers, a healthy subject population with carefully considered inclusion/exclusion criteria will ensure that subjects are fit and well enough for participation in the study.

The following eligibility criteria are designed to select subjects for whom protocol treatment and procedures are considered appropriate. All relevant medical and non-medical conditions should be taken into consideration when deciding whether this protocol is suitable for a particular subject.

### **6.1. Inclusion Criteria**

#### **6.1.1. To be Confirmed at Screening**

1. Regular moderate cigarette smokers (minimum 10 cigarettes per day) who want to stop smoking.

2. Urine cotinine >500 ng/mL.
3. Expired air carbon monoxide (CO) > 11 parts per million (no cigarette 1 hour before test).
4. Healthy males and females 18-65+ years of age.
  - a. If a female subject of child bearing potential, a negative pregnancy test at screening and admission and willing to use an effective method of contraception (unless of non-childbearing potential or where abstaining from sexual intercourse is in line with the preferred and usual lifestyle of the subject) from first dose until 3 months after last dose of cytisine.
  - b. If a female subject of non-child bearing potential, a negative pregnancy test at screening and admission. For the purposes of this study, this is defined as the subject being amenorrheic for at least 12 consecutive months or at least 4 months post-surgical sterilisation (including bilateral fallopian tube ligation or bilateral oophorectomy with or without hysterectomy). Menopausal status will be confirmed by demonstrating at screening that levels of follicle stimulating hormone (FSH) fall within the respective pathology reference range. In the event a subject's menopause status has been clearly established (for example, the subject indicates she has been amenorrheic for 10 years), but FSH levels are not consistent with a post-menopausal condition, determination of subject eligibility will be at Investigator's discretion following consultation with the Sponsor.
  - c. If a male subject, willing to use an effective method of contraception (unless anatomically sterile or where abstaining from sexual intercourse is in line with the preferred and usual lifestyle of the subject) from first dose until 3 months after last dose of cytisine.
5. Subject with no clinically significant abnormal serum biochemistry, haematology and urine examination values within 28 days before the first dose of cytisine.
6. Subject with negative urinary drugs of abuse screen, determined within 28 days before the first dose of cytisine (a positive alcohol result may be repeated at Investigator's discretion).
7. Subject with negative human immunodeficiency virus (HIV), hepatitis B surface antigen (Hep B) and hepatitis C virus antibody (Hep C) results.
8. Subject with no clinically significant abnormalities in 12-lead ECG determined after minimum of 5 minutes in supine position within 28 days before the first dose of cytisine.
9. Subject with no clinically significant abnormalities in vital signs (systolic blood pressure between 90-150 mmHg (age 18-65) and 90-160 mmHg (age >65), diastolic blood pressure (DBP) between 50 and 90 mmHg, and pulse rate (PR) between 40-110 bpm, measured on the dominant arm after minimum of 5 minutes in supine position) determined within 28 days before first dose of cytisine.
10. Subject must be available to complete the study (including in-clinic stays and post study follow-up) and comply with study restrictions.
11. Subject must provide written informed consent to participate in the study.

### **6.1.2. To be Re-Confirmed Prior to Start of Dosing (Day -1)**

1. Subject continues to meet all screening inclusion criteria (before the first dose only).
2. Subject has a negative urinary drugs of abuse screen (including alcohol).
3. Female subject has a negative pregnancy test.

## **6.2. Exclusion Criteria**

### **6.2.1. To be Confirmed at Screening**

1. Treatment with smoking cessation medications (bupropion, varenicline, any nicotine replacement therapy) within 8 weeks of first dose of cytisine.
2. Use of other forms of nicotine (e-cigarettes, smokeless tobacco) within 8 weeks of first dose of cytisine or are planning to use these products during study.
3. Known hypersensitivity/allergy reaction to varenicline, other cytisine-derivatives or any of the excipients in the [REDACTED] formulation.
4. History of severe hypersensitivity reactions to any other drugs.
5. Current treatment with antihypertensive medicinal products, statins, tuberculostatics, cholinomimetics or anticholinesterase medicinal products.
6. History of any medical condition (e.g. gastrointestinal, renal or hepatic) or surgical condition (e.g. cholecystectomy, gastrectomy) that may affect drug pharmacokinetics (absorption, distribution, metabolism or excretion).
7. Female subjects who are breast feeding.
8. Difficulty in donating blood on either arm or known history.
9. History of alcoholism or drug abuse within last 2 years.
10. Use of non-prescription drugs, including vitamins, herbal and dietary supplements within 14 days (or 5 half-lives, whichever is longer) prior to the first dose of cytisine, unless in the opinion of the Principal Investigator the medication will not interfere with the study procedures or compromise subject safety.
11. Participated in any investigational drug clinical trial within the previous 3 months or a marketed drug trial within the previous 30 days prior to randomisation on Day 1.
12. Donation of 450 mL or more blood or had history of significant blood loss due to any reason or had plasmapheresis within 3 months before the first dose of cytisine.
13. Inability to communicate well with Principal Investigator or designees (i.e., language problem, poor mental development or impaired cerebral function).
14. Any other condition that the Principal Investigator considers making the subject unsuitable for this study.

### **6.2.2. To be Re-Confirmed Prior to Start of Dosing (Day -1):**

1. Development of any exclusion criteria since screening.

2. Use of non-prescription drugs, including vitamins, herbal and dietary supplements since screening, unless in the opinion of the Principal Investigator or designee the medication will not interfere with the study procedures or compromise subject safety.
3. Participation in a clinical study since the screening visit.
4. Donation of 450 mL or more blood since the screening visit.

### **6.3. Removal of Subjects from Therapy or Assessment**

Each subject will be informed of their right to withdraw from the study at any time and for any reason.

The Principal Investigator will withdraw a subject from the study at any time for any of the following reasons:

- If a subject experiences a serious or intolerable AE, that prevents them from continuing.
- If a subject incurs a significant protocol violation which impacts on their safety or the scientific integrity of the study (this will be discussed on a case-by-case basis with the Sponsor).
- At the request of the Sponsor.
- If it is considered that the subject's health is compromised by remaining in the study or the subject is not sufficiently cooperative.
- If a subject is lost to follow-up.

The reasons for any subject withdrawal will be recorded on the study completion form of the case report form (CRF).

If a subject is withdrawn or chooses to withdraw from the study for any reason, every possible effort will be made to perform the evaluations described for the post-study follow-up. The data collected from withdrawn subjects will be included in the study report.

In the event of any abnormalities considered to be clinically significant, subjects will be followed up with appropriate medical management until values are considered to be clinically acceptable. Referral or collaborative care will be organised if considered necessary.

Since 36 subjects are required to complete the study, subjects who withdraw from the study before receiving any study medication will be replaced. Subjects who are withdrawn from the study due to significant drug-related AEs will not be replaced. Replacement of all other subjects withdrawn from the study after receiving study medication will be decided on a -case-by-case basis by the Principal Investigator (or designee) and Sponsor.

## **7. RESTRICTIONS PRIOR AND DURING THE STUDY**

To avoid possible negative effects on the measurement of plasma drug concentrations and/or on subject's safety, several restrictions are to be adopted as outlined in the eligibility criteria and in the following sections.

## **7.1. Confinement**

Each subject will be required to provide a total of 9 overnight stays in the clinic over a 26-day period.

## **7.2. Smoking, Diet and Fluid Restrictions**

### **7.2.1. Smoking**

There will be minimal restrictions to smoking during days of confinement, such as all smoking must occur within designated area(s) only and subjects cannot smoke during active PK sampling period (i.e. subjects must have their last cigarette a minimum of 2 hours before dosing and can only start smoking after final PK sample). Subjects will go for a cigarette as a group and will need to have their last cigarette before 23:00 while they stay in the clinic. Clinic staff will review these guidelines with subjects during confinement and will monitor compliance.

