### **8.8. Selection and Timing of Dose for Each Subject**

First dose will be administered at approximately 9.00 a.m. on Day 1. Additional doses will be as per the Dosing Schedule (see [Figure 4](#)). A target time will be provided for each dose in the diary and actual time of dose will be recorded. For Days where dosing is every 2 to 3 hours, dosing should be  $\pm$  10 min within the targeted time. For Days where dosing is every 4-6 hours, dosing should be  $\pm$  30 min within the targeted time.

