### **15.9.1. Holter ECGs**

The following ECG parameters will be extracted in triplicate from Holter recordings on Day 1 and Day 25 at 30 and 15 minutes prior to the first dose and 0.5 h, 1 h, 2 h, 3 h, 4 h, 6 h, 8 h, 12 h and 24 h post dose:

- Heart Rate (HR)
- PR intervals
- QRS
- QT
- QTcF

If a large change in heart rate is observed during the study, the individual QT correction method (QTcI) will be used as the primary QT correction method.

The extracted ECG parameters will be listed with any out of normal range values flagged (“H” -high or “L” -low). The ECG results will be assessed as either “normal” or “abnormal”. Any comments on abnormal results will also be provided. Descriptive statistics of absolute and change from baseline values at each time point will be tabulated by dose group and age group (18-65, >65 and overall).

In addition, frequencies of QTcF data will be calculated according to the following categories:

For absolute values:

- $QTcF \leq 450$  mSec
- $450 < QTcF \leq 480$  mSec
- $480 < QTcF \leq 500$  mSec
- $QTcF > 500$  mSec.

For change from baseline:

- QTcF increase  $\leq 30$  mSec
- $30 < QTcF$  increase  $\leq 60$  mSec
- QTcF increase  $> 60$  mSec.

Abnormalities in ECGs will be classified in terms of clinical significance. Clinically significant abnormalities will be reported as AEs. The number and percentage of subjects developing new ECG abnormalities will be summarised. The presence of outliers will be explored for heart rate, PR, QRS, QT and QTcF. Details of this analysis will be described in the Statistical Analysis Plan (SAP).

In order to explore the effects of cytisine on QTc prolongation, plasma concentrations will be plotted against change from baseline QTcF values.

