11.4.1 Plasma Concentration Data

Plasma PK samples will be collected for measurement of cytosine at the following time points:

- Day 1, first dose: Pre-first dose, 0.5h, 0.75h, 1h, 1.25h, 1.5h, 2h;
- Day 1, last dose: Pre-last dose, 0.5h, 1h, 1.5h, 2h, 2.5h, 3h, 3.5h, 4h, 5h;
- Days 2 and 3: Pre-last dose, 0.5h, 1h, 1.5h, 2h, 2.5h, 3h, 3.5h, 4h, 5h;
- Days 4, 13, 17, 21: Pre-first dose;
- Days 12, 16, 20, 24: Pre-last dose, 1h, 1.5h, 2h, 2.5h, 3h, 3.5h, 4h;
- Day 25: Pre-dose, 0.5h, 0.75h, 1h, 1.25h, 1.5h, 1.75h, 2h, 2.25h, 2.5h, 2.75h, 3h, 3.25h, 3.5h, 3.75h, 4h, 5h, 6h, 8h, 10h, 12h, 24h.

Cytosine concentrations in plasma will be listed and summarised by dose group and age group using the descriptive statistics N, n, arithmetic mean, arithmetic standard deviation (SD), coefficient of variation (CV%), minimum, median and maximum.

The individual subject plasma cytosine concentration profiles over time will be presented graphically using actual blood sampling times on a linear and semi-logarithmic scale. Arithmetic mean plasma cytosine concentration profiles over time will be presented on linear and semi-logarithmic scales with profiles presented for each study day as appropriate and a separate plot for each dose group and age group.

For inclusion within the summary tables and linear scale plots, concentrations below the limit of quantification (BLQ) will be assigned a value of zero. For inclusion within the semi-logarithmic scale plots, concentrations below the limit of quantification (BLQ) will be set to missing. Concentrations above the upper limit of quantification (ULOQ) will be obtained via dilution into the calibration range and are valid results.

Plasma concentration data listings and individual plots will be presented using the Safety Set. Plasma concentration data summaries and mean plots will be presented using the PK Set and the Safety Set. All plasma concentration data included in listings and summaries will be presented to three significant figures.

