11.6.4.2 Holter Monitoring

The ECG extraction time points will be from extraction windows which precede the PK blood draws. ECG parameters (heart rate, PR interval, QRS duration, QT interval and QTcF interval) will be extracted in triplicate from Holter recordings on Day 1 and Day 25 at 30 and 15 minutes prior to the first dose and at 0.5h, 1h, 2h, 3h, 4h, 6h, 8h, 12h and 24h post dose.

The extracted ECG parameters will be listed with any out of normal range values (see Appendix 1) flagged (flag 'H' or 'L' appended to relevant result). The ECG results will also be assessed as either 'normal' or 'abnormal' with comments on abnormal results also presented.

The mean of the triplicate recordings at each time point will be calculated for use in the summary tables and plots. Any ECG traces that are determined to contain a technical error will not be included in the calculation of the mean values. At each time point, the mean value will be derived from all ECGs (generally three) that are free of technical errors. Descriptive statistics (N, n, mean, SD, minimum, median and maximum) of absolute and change from baseline (see definition, Section 5) values on Day 1 and Day 25 at each time point up to 24h, will be tabulated for each dose group and age group. The change from baseline ECG results will also be plotted over time by dose group and age group.

In addition, frequencies of QTcF data will be calculated according to the following categories:

For absolute values:

- QTcF > 450 mSec
- QTcF > 480 mSec
- QTcF > 500 mSec

For change from baseline:

- QTcF increase > 30 mSec
- QTcF increase > 60 mSec.

The presence of outliers will be explored for heart rate, PR interval, QRS duration, QT interval and QTcF interval). The outlier analysis will use the time-averaged baseline (see definition, Section 5) and compare that baseline value to each of the individual on-treatment ECG time point values. Outliers are defined as follows for this analysis:

- Heart rate: A value for a subject will be considered to be an outlier at a pre-defined post dose time point if the heart rate measurement at that time point is <50 bpm and the measure is at least a 25% decrease from the subject's baseline mean heart rate (i.e., a bradycardic event) or if the heart rate measurement at the pre-defined post dose time point is >100 bpm and the measure is at least a 25% increase from the baseline mean heart rate (i.e., a tachycardic event).

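### Smoking is barred only around PK sampling, so the Day 1 Holter extractions at 3, 4, 6 and 24 h (8 h on the boundary) can directly follow a cigarette whose time is not recorded

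*Protocol*

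**What the plan says.** Protocol 7.2.1 sets a light rule for confinement: "There will be minimal restrictions to smoking during days of confinement". The exception is the active PK sampling period, when "subjects must have their last cigarette a minimum of 2 hours before dosing and can only start smoking after final PK sample". Subjects also "will need to have their last cigarette before 23:00 while they stay in the clinic"; no time is given at which smoking may resume in the morning. Subjects smoke as a group and staff monitor compliance.

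The Holter times are the same on Day 1 and Day 25: 30 and 15 minutes before the first dose, then "0.5 h, 1 h, 2 h, 3 h, 4 h, 6 h, 8 h, 12 h and 24 h post dose" (Protocol 15.9.1, repeated in SAP 11.6.4.2). SAP section 5 defines one Holter baseline, the mean of the two Day 1 pre-dose times, for the change from baseline on both days.

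The PK schedule in SAP 11.4.1 sets the smoke-free periods. It gives "Day 1, first dose: Pre-first dose, 0.5h, 0.75h, 1h, 1.25h, 1.5h, 2h" and, separately, "Day 1, last dose: Pre-last dose, 0.5h, 1h, 1.5h, 2h, 2.5h, 3h, 3.5h, 4h, 5h". Day 2 is sampled only around its last dose. Day 25 is sampled from pre-dose to 24 h.

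The Holter sections (Protocol 13.8 and 15.9.1, SAP 11.6.4.2) add no smoking rule. The diary (Protocol 13.9) and the visit procedures (Protocol 11.2.3) collect the number of cigarettes. Doses are recorded with clock times; cigarettes are not.

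**The concern.** QT/QTc and cardiac safety is a secondary objective (Protocol 4.2). There is no placebo arm, so the change from the Day 1 baseline carries the inference. If some post-dose extractions can come minutes after a cigarette and the baseline cannot, any acute effect of smoking on heart rate enters those time points and looks like a drug effect.

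Three features make this more than a formality. Protocol 2.4 says the drug's possible undesirable effects are mainly nicotine-like, so smoking and drug effects may be hard to tell apart by type. The open window on Day 1 also coincides with dosing about every 2 h. Finally, the protocol would have used an individual QT correction if heart rate changed greatly, and SAP 1.2 removes it as not feasible, which leaves QTcF alone.

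**Working it through.** **The plan's own figure.** The PK schedule fixes the smoke-free periods, so I checked it first. Samples by period: 7 + 10 + 10 + 10 + 1 + 8 + 1 + 8 + 1 + 8 + 1 + 8 + 22 = 95, and 95 × 3.0 mL = 285 mL. Both agree with Protocol 12.1.

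**Inputs**
- "First dose will be administered at approximately 9.00 a.m. on Day 1" (Protocol 8.8).
- Six doses about 2 h apart on Day 1 (Protocol Figure 4), so the last dose is at 5 × 2 = 10 h, about 19:00.
- Bar around each sampled dose: from dose − 2 h to the final PK sample of that period (Protocol 7.2.1).
- Extraction windows precede the blood draws (SAP 11.6.4.2), so the 2 h extraction on Day 1 and the 24 h extraction on Day 25 fall inside the bar.

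**Barred periods, in hours from the first dose**
- Day 1, first dose: −2 to 2 h (07:00 to 11:00).
- Day 1, last dose: 10 − 2 = 8 h to 10 + 5 = 15 h (17:00 to 24:00). The 23:00 curfew then covers the night.
- Open: 2 to 8 h (11:00 to 17:00), and the morning of Day 2, whose first dose has no PK sampling.
- Day 25: −2 to 24 h.

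**Shortest gap between a permitted cigarette and each extraction**

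| Extraction | Day 1 | Day 25 |
|---|---|---|
| −30 min | 1.5 h | 1.5 h |
| −15 min | 1.75 h | 1.75 h |
| 0.5 h | 2.5 h | 2.5 h |
| 1 h | 3 h | 3 h |
| 2 h | 4 h | 4 h |
| 3 h | about 0 | 5 h |
| 4 h | about 0 | 6 h |
| 6 h | about 0 | 8 h |
| 8 h | about 0 (boundary) | 10 h |
| 12 h | 4 h | 14 h |
| 24 h | about 0 | 26 h |

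Four Day 1 points are clearly open (3, 4, 6, 24 h) and 8 h sits on the boundary: 4 to 5 of 9, against 0 of 9 on Day 25.

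**Sensitivity of the count.** If the last dose is 10 minutes early (the tolerance in Protocol 8.8), the 8 h gap becomes 10 minutes. If doses are 1.9 h apart, the last dose is at 9.5 h, the bar starts at 7.5 h, and the 8 h gap is 0.5 h. With doses 2 h apart, the list of open points is the same for any definition of recent smoking up to 1.5 h.

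**Which outputs are reached.** On Day 1 the Holter times with a matching PK sample are 0.5, 1 and 2 h, and 12 h (10 + 2). The points at 3, 4, 6, 8 and 24 h have no matching concentration and cannot enter the concentration-QTcF plot of SAP 11.7. They do enter the by-time change-from-baseline summaries and plots.

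**Illustration of size, on assumed inputs.** The documents give no smoking effect. Suppose heart rate moves from 65 to 75 bpm (RR 0.923 to 0.800 s), QTc is near 400 ms, and the true QT-RR exponent b is 0.25 to 0.40 instead of 1/3. The shift in QTcF is 400 × [0.800^(b − 1/3) − 0.923^(b − 1/3)], which is +4.8 ms for b = 0.25 and −3.8 ms for b = 0.40. Even the sign depends on the assumption.

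**The case against.** **The reading of the rule.** If the final PK sample means the last sample of the day, Day 1 is smoke-free from 07:00 to midnight and only the 24 h extraction is open, 1 of 9. This reading is possible. It is the less natural one, because Protocol 11.2.3 and Table 7 treat the two Day 1 periods separately and 7.2.1 describes its restrictions as minimal. The ambiguity stands and needs a clarifying sentence. On Day 25 the literal rule means 26 h without smoking, yet Protocol 11.2.11 still records cigarettes that day, so full protection there rests on the rule being applied as written.

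**The threshold tables.** A reader might infer that the outlier and category tables are distorted. The illustration does not support that. The tachycardia outlier in SAP 11.6.4.2 needs more than 100 bpm and at least a 25% rise; 65 to 75 bpm is a 10/65 = 15% rise to 75. The QTcF categories start above 450 ms or at an increase above 30 ms. Only a larger shift, or a subject already near a boundary, would change those tables.

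**Day 1 against Day 25.** A reader might infer that smoking is what makes the two days non-comparable. SAP 11.6.4.2 summarises each day against one baseline and plans no contrast between them. The days already differ by design: fasted against fed before the first dose, and six doses against one.

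**Bias between doses.** A reader might also infer that the bias differs by dose because one dose cuts smoking sooner. Dose is randomised, and nothing in the documents suggests a difference in smoking within 24 h of the first dose.

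**Scale.** The QT objective is exploratory and descriptive, with no hypothesis test planned. That limits the weight of the point but does not remove the confounding.

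**Conclusion.** The point holds in a limited form. On the natural reading of Protocol 7.2.1, 4 to 5 of the 9 Day 1 post-dose extractions can directly follow a cigarette, while the baseline is at least 1.5 h clear and the Day 25 extractions are protected to 24 h. Without a placebo arm or cigarette times, a smoking effect cannot be separated from a drug effect in the Day 1 by-time change-from-baseline summaries and plots of heart rate and QTcF.

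The count assumes doses about 2 h apart and a bar that ends with each sampling period; on the other reading it falls to 1 of 9. The size of any bias in bpm or ms cannot be derived from the documents, and the sign of a QTcF bias is open. It would be too broad to say that smoking is mixed into the QTc results as a whole, since the concentration-QTcF plot does not use the exposed points. This is a real, cheaply reduced confounder in an exploratory safety summary; it does not undermine the study.

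**What to change.** 1. In Protocol 7.2.1, state whether the bar ends at the last sample of each sampling period or of the day.
2. Record the clock time of each cigarette on Day 1 and on the morning of Day 2. Subjects smoke as a group under staff supervision, so logging each smoking break is enough.
3. In SAP 11.6.4.2, flag extractions that fall within a pre-set interval after smoking and add a sensitivity summary of the heart-rate and QTcF changes that excludes them. An interval of 1 h would match the gap already used for the CO test in inclusion criterion 3, but the documents give no basis for it as a heart-rate washout, so it is a convention to be fixed in advance.
4. If times cannot be collected, limit the sensitivity summary to the protected Day 1 points: 0.5, 1, 2 and 12 h. That version says nothing about 3 to 8 h.

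The cost is one CRF field and one extra table.

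I would not add a smoking bar before each extraction. A 1 h bar would cut the open 2 to 8 h window from six hours to about two (4 to 5 h and 6 to 7 h). It would force down Day 1 cigarette consumption, a measure under a primary objective, to protect a secondary descriptive one.
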